 Attributes	 Personnel
 Funding	 Background
 Research Aims and Abstracts	 Procedures

IRB-AAAQ1758

Page 1 of 26

- Locations
 Data Security and Privacy
 Informed Consent/Recruitment
 No revisions to submission content required
- Subjects
 Risks/Benefits/Monitoring
 Attachments (including Rascal-generated attachments)

Has the consent form been revised in this submission?

No

Does this modification include only administrative changes?

No

Attributes

Special review type: Check all that apply or check "None of the Above" box.

- Review for 45 CFR 46.118 Determination (involvement of human subjects is anticipated but is not yet defined)
 Funding review for Administrative IRB approval (such as for Center or Training Grants)
 None of the above

IRB of record information: Will a Columbia IRB be the IRB that is responsible for providing review, approval, and oversight for this study?

Yes

Select the most appropriate response:

Columbia will be the IRB of record for the study procedures conducted by Columbia researchers (Note: this response will apply to most submissions).

Is this research part of a multicenter study?

No

Please indicate if any of the following University resources are utilized:

- Cancer Center Clinical Protocol Data Management Compliance Core (CPDM)
 CTSA-Irving Institute Clinical Research Resource (CRR)
 CTSA- Irving Institute Columbia Community Partnership for Health (CCPH)
 None of the above

Background

Abbreviated Submission:

The IRB has an abbreviated submission process for multicenter studies supported by industry or NIH cooperative groups (e.g., ACTG, HVTN, NCI oncology group studies, etc.) and other studies that have a complete stand-alone protocol. The process requires completion of all Rascal fields that provide information regarding local implementation of the study. However, entering study information into all of the relevant Rascal fields is not required, as the Columbia IRBs will rely on the attached stand-alone (e.g., sponsor's) protocol for review of the overall objectives.

If you select the Abbreviated Submission checkbox and a section is not covered by the attached stand-alone protocol, you will need to go back and provide this information in your submission.

Study Purpose and Rationale:

Provide pertinent background description with references that are related to the need to conduct this study. If this is a clinical trial, the background should include both preclinical and clinical data. Be brief and to the point.

[] Abbreviated Submission - This information is included in an attached stand-alone protocol. Proceed to the next question

Fatigue is among the most prevalent, debilitating, and refractory symptoms of multiple sclerosis (MS),¹⁻³ a chronic autoimmune inflammatory disease affecting approximately 400,000 Americans that is typically diagnosed during young or middle adulthood. As one of my MS patients described fatigue: *"It's like having a wet blanket over my shoulders all day long."* For persons with MS, fatigue limits functional independence and encumbers successful achievement of normative goals such as gainful employment and raising a family.⁴ Despite much empirical and clinical attention, the underlying mechanism(s) of fatigue are poorly understood. Investigations seeking a neuroanatomical basis for MS fatigue using MRI have produced equivocal results,⁵⁻¹⁴ with some studies finding no links,⁵⁻⁸ and others linking MS fatigue to such varied parameters as lesion load,^{12,13} corpus callosum atrophy,⁹ parietal atrophy,^{6,10,12} frontal atrophy,^{10,12} deep gray atrophy,^{10,14} and generalized cerebral atrophy.^{11,13} These inconsistent, non-specific findings perpetuate uncertainty about the etiology of MS fatigue as well as highlight the likelihood that multiple etiologies underlie MS fatigue. This notion is supported by the heterogeneity of patients' own descriptions of fatigue: some report stable fatigue, while others note day-to-day fluctuations. We currently lack effective treatments for fatigue. Although many patients are prescribed stimulant medication (e.g., modafinil) (likely based on the assumption that fatigue is linked to arousal dysfunction), several randomized clinical trials have failed to support their efficacy to reduce fatigue in MS.¹⁵⁻¹⁸ In contrast, cooling treatments (e.g., cooling garments^{19,20}, antipyretics^{21,22}) have shown promise for reducing MS fatigue. These treatments have yet to be widely embraced, perhaps because underlying mechanisms to support this approach have not been elucidated. **We recently published the first-ever report of elevated body temperature in relapsing-remitting MS (RRMS) patients relative to healthy controls, and elevated temperature was linked to worse fatigue.**²³ Importantly, we have also replicated our original finding in a separate sample collected in Milan, Italy.²⁴ Our observation of higher body temperature in MS is completely novel, although it may not seem that way. Mention of temperature and the first thing called to mind is 'Uthoff's phenomenon': Wilhelm Uthoff's observation in 1890 that MS patients show worse symptoms after heat exposure.²⁵ This observation motivated a comprehensive body of research to experimentally manipulate/raise body temperature in MS patients to observe worse clinical symptoms.²⁶⁻³⁷ Despite all this work, what has been surprisingly missing from the literature until now was an investigation of core body temperature *in the absence of experimental manipulation*. **Our finding that body temperature is elevated and linked to fatigue in RRMS lays the groundwork for a paradigm shift in our understanding and treatment of fatigue.** That is, we shift our focus from exogenous to endogenous temperature, and from stimulant medication to cooling treatments. The current pilot project will interrogate our temperature hypothesis of fatigue in the following ways: 1) establish a link between elevated brain temperature and fatigue, 2) test aspirin as a novel cooling treatment for fatigue in MS targeting elevated body/brain temperature, and 3) explore the impact of reduced brain temperature on efficiency of neural network function using fMRI resting-state functional connectivity analysis. Elevated brain temperature was recently reported in MS patients compared to healthy controls,^{38,39} although no study has ever investigated its association to fatigue or its impact on neural network efficiency in MS, or in any clinical

population. Brain temperature can be easily and non-invasively measured using a simple sequence on MRI, magnetic resonance spectroscopy (MRS).^{40,41} MRS is easily acquired with MRI and can be used to derive brain temperature with accuracy of $\pm 0.1^{\circ}\text{C}$.⁴⁰ Additional advantages of MRS thermometry are that it can be acquired within the context of a standard clinical scan, and it does not require the use of contrast. Brain temperature provides valuable prognostic information for a growing number of clinical populations (e.g., acute ischemic stroke,^{42–44} neonates with hypoxic-ischemic encephalopathy⁴⁵), although MRS thermometry has been employed in only one MS study to date (revealing elevated brain temperature³⁸). As a feasibility study, we used MRS thermometry to measure brain temperature in 14 MS patients and found a link between brain temperature and fatigue .

Exercise has many benefits for persons with multiple sclerosis (MS), and decreased participation in exercise may put MS patients at risk for disability secondary to a sedentary lifestyle. Therefore, encouraging MS patients to exercise is a key priority for clinicians. The challenge to widespread endorsement of exercise is that many MS patients experience exercise-induced short-term discomforts of overheating and exhaustion. In healthy people, exercise causes an increase in core body temperature, which in turn leads to reduced performance. A recent study comparing healthy adults to adults with MS showed that whereas exercise increased body temperature in both groups, only in the MS group was it correlated with exhaustion. The reason for this may relate to our first-ever observation that resting body temperature is elevated in relapsing-remitting MS (RRMS) patients relative to healthy controls. That is, even before being exposed to heat or exercising, people with RRMS are already warmer (note that this is distinct from Uhthoff's phenomenon, which exclusively relates to exogenous heat exposure rather than endogenous core body temperature). Our finding is clinically meaningful, as elevated body temperature was correlated with worse fatigue in our patients. This link provides novel context for several prior successful trials of cooling treatments (e.g., cooling garments, aspirin) for reducing fatigue in MS patients outside of exercising. Likewise, novel but cumbersome cooling treatments (e.g., cooling chambers) administered during exercise in MS have improved exercise performance. This pilot project is the first study of aspirin (acetylsalicylic acid, ASA) as a cost-effective, readily-available, and easily-administered pretreatment before exercise in RRMS to reduce overheating and exhaustion. Exercise Aim: To determine whether pretreatment with ASA (compared to placebo: withinsubject crossover design) before exercise results in improved exercise performance (i.e., increased time-to-exhaustion). We hypothesize that participants will tolerate exercise for longer after taking ASA than placebo. This hypothesis is based on a) demonstrated efficacy of antipyretic for reducing body temperature during exercise in healthy controls, b) demonstrated efficacy of antipyretic for reducing fatigue in non-exercising MS patients, and c) demonstrated efficacy of elaborate (unblinded) cooling treatments (e.g., cooling garments, cooling hand chamber) for improving exercise performance in MS patients. Note that this project is especially important for MS patients, who have a disease-specific body temperature elevation and sensitivity to heat (i.e., Uhthoff's).


Describe the methodology that will be used in this study, covering such factors as retrospective vs. prospective data collection, interventional vs. non-interventional, randomized vs. non-randomized, observational, experimental, ethnography, etc.

[] Abbreviated Submission - This information is included in an attached stand-alone protocol. Proceed to the next question

All MS participants will undergo the following procedures: I. Participants will be asked to refrain from eating for 2 hours prior to their arrival at our center. Once here, after the consenting process is finished, participants will have their temperature taken aurally (two measurements will be taken for reliability) and will then complete a simple motor task, the hand dynamometer test (5 measurements will be taken), an objective measure of physical fatigue that has been used in MS (Greim et al, 2007). They will then have their aural temperature measured again, before filling out questionnaires on fatigue (FSS, VAS), mood (BDI-II), and a diary page. Aural temperature will be recorded once again, just before the pill is administered (placebo or aspirin). II. Scan condition: Participants are then scanned for one hour. Immediately after scanning, aural temperature is recorded, followed by the same set of questionnaires, plus one additional questionnaire, the Global Fatigue Change (GFC). All participants will also be asked which pill they think they received, aspirin or placebo. The hand dynamometer test will be completed once again, followed by a final aural temperature measurement. All of these procedures are expected to take under 2 hours. III. Patients who are not scanned will wait quietly for one hour, and then baseline procedures will be repeated [temperature taken aurally (two measurements will be taken for reliability), repeat the hand dynamometer test, complete questionnaires on fatigue (FSS, VAS)]. Exercise condition: Ten RRMS patients will be randomized in a crossover double-blind study. After undergoing same procedures as above (section I), each subject in the exercise condition will undergo the following additional procedures: subject will have peak ventilatory capacity (Maximum Voluntary Ventilation, MVV) determined before the exercise test via a Vmax Encore System (CareFusion Corp, San Diego, CA). Each subject will have a 5-minute resting phase followed by a three-minute warm up and then a progressive ramped exercise test using a VIA Sprint 150P lower body cycle ergometer (CareFusion Corp, San Diego, CA) until achieving one of the following VO₂max criteria: respiratory exchange ratio (RER) 1.1, increases in ventilation without concomitant increases in VO₂, maximum age predicted heart rate and/or volitional fatigue. An individualized ramping protocol will be used as determined by weight and subject's exercise profile as determined by a certified exercise physiologist. Blood pressure, tympanic temperature, and RPEbr and RPElegs data will be collected at 3-minute intervals. Minute ventilation, expired oxygen (O₂), carbon dioxide (CO₂), watts, RER, and total time will be measured using Vmax Encore Metabolic system (Sensormedics, Inc, Loma Linda, CA). Flow sensor and gas analyzer will be calibrated against known medical grade gases before each test. VO₂max will be determined from peak 20-second average of the breath-by-breath measurement of VO₂. Identical test procedures will be carried out after initiation of placebo or ASA. Anaerobic threshold will be determined for each subject using the V-slope technique. The exercise test will commence one hour after pill was administered. Exercise test: Patients will maintain a cycle cadence between 50-60 revolutions per minute (RPM) on the lower body cycle ergometer for the duration of the test. The test will be terminated when the cadence drops below 40 RPM for 5 seconds, or when participant reaches volitional exhaustion [i.e., in the presence of American Thoracic Society (ATS) standard test termination criteria]. In healthy adults, the estimated time to bring about volitional exhaustion is 8-12 minutes. At termination, RPEbr, RPEleg, blood pressure (BP), and tympanic

temperature (right ear) will be recorded (BODY TEMP 2). In addition, participants will record their current level of fatigue with VAS of fatigue and Global Fatigue Change (GFC). Each exercise session will be performed at the same time of day (± 1 hour), and between the hours of 11 am and 5 pm. The temperature of the room will be held constant to within ± 5 degrees Fahrenheit, and recorded at the start of each session. After each phase (placebo and ASA), participants will be asked which condition they think they were in, to ensure effectiveness of blinding. A sample of 12 healthy controls will be enrolled to obtain normative brain temperature. The HC group procedures will be as follows: After being consented, participants will fill out a BDI-II, FSS, VAS, and a diary page. They will have aural temperature measured before being scanned. After the scan, aural temperature will be measured once again, before participants are asked to fill out questionnaires once again: FSS, VAS, GFC. These procedures are expected to take approximately one hour total.

Statistical Procedures:

Provide sufficient details so that the adequacy of the statistical procedures can be evaluated including power calculations to justify the number of participants to be enrolled into the study. Definitions of subject terms such as enrolled and accrued as used for Rascal submissions can be found in the Subjects section.

[] Abbreviated Submission - This information is included in an attached stand-alone protocol. Proceed to the next question

Methods and Statistical approach: Scan condition: All participants will be scanned at New York State Psychiatric Institute at CUMC in consultation with [name] (Co-I, Senior Physicist and Director of physics and engineering), who assisted in MRS analysis of the feasibility data presented here. Aim 1. We will examine the association of brain temperature in centrum semiovale (all neuroanatomical sites were selected consistent with 38) and fatigue (FSS total score) using a partial correlation controlling for sex, age, and depression (BDI-II total score, consistent with 23). Secondary analyses will be conducted using brain temperature in calcarine sulcus and lesion site, and fatigue measured with the MFIS (total score, subscale scores), and VAS of pain, mood, and fatigue. Aim 2. Our primary analysis will determine whether aspirin administration is effective for reducing brain temperature. A 2x2 mixed ANOVA will be run with factors of group (placebo vs. aspirin) and time (Pre vs. Post). Post-hoc tests of all significant effects will be run. A secondary analysis will investigate the impact of aspirin on fatigue. The same 2x2 mixed ANOVA will be run, with VAS of fatigue as the dependent measure. Aim 3: Functional Connectivity analysis. Data preprocessing will be performed with AFNI and the FMRIB Software Library (e.g., 52, 53). A recent fMRI RSFC study identified seven primary brain networks in 979 healthy adults, identifying a central "hub" for each network (component of each network most functionally integrated with the rest of the network).⁵⁴ Guided by the results of this large-scale study, we will place spherical 6-mm radius seed ROIs within the hub of each network. RSFC will thus be derived for each network (consistent with our methods as described in 57). For the full sample (N=20), regressions will be conducted to examine the association of brain temperature and FC within each network. We expect higher brain temperature to be associated with lower FC, particularly in networks previously seen to be impacted by fatigue (e.g., sensorimotor network).⁵⁰ For our analysis of the aspirin subgroup, a 2x2 mixed ANOVA will be run with factors of group and time to identify FC changes from Pre to Post, which we expect in the aspirin group relative to the placebo group. We expect that aspirin (versus placebo) will increase network connectivity from pre- to post-scan. Finally, support our hypothesis that such changes are due to changes in brain temperature, we will investigate whether the degree of change in network efficiency is correlated with degree of brain temperature change within the aspirin group using 3D regression within AFNI. Exercise condition. This is a within-subject, 2 (ASA, placebo) by 2 (Time 1, Time 2) cross-over trial in which each subject will serve as his/her own control. Subjects will be randomized to one of two sequences: the

first group will receive ASA at the first exercise session and placebo at the second, while those in group 2 will receive placebo at the first session and ASA at the second. Data analysis will proceed as follows. First, all variables will be inspected for outliers or inconsistent values. Variables that display an extremely right skewed distribution with outliers will be transformed using the log transformation. Any remaining outlier values will be dealt with using winsorization, i.e. the extreme values will be censored down to the nearest non-outlier value. Aim: We hypothesize that participants will demonstrate longer time-to-exhaustion after receiving ASA than after receiving placebo (within-subject crossover design). The measure of interest is the length of time (i.e., time-to-exhaustion) spent exercising at each session. This time has no pre-set upper limit, i.e. patients are free to exercise as long as they wish. This means that the time will not be censored. The effects in a balanced 2x2 crossover trial with treatments A and B with outcome measures YAB and YBA in the two groups, respectively, where A and B are the population means for the direct effects of treatments A and B, respectively, represents a sequence effect, represents a session effect, and A and B represent carryover effects of treatments A and B, respectively. Because ASA has only a short-term effect and the wash-out period is more than adequate, we expect no carryover effects. However, we will still test for carryover effects using the test statistic in Wellek et al. Test for differences between treatment effects: The appropriate test statistic will be an unpaired t statistic on the within-subject differences in outcome between Session 1 and Session 2 (in this order), comparing sequence group AB: $YAB_{1i} - YAB_{2i}$, and sequence group BA: $YBA_{1j} - YBA_{2j}$, over all subjects $i=1, \dots, n_1$ and $j=1, \dots, n_2$. Significance level for the difference will be reported using the probabilities from the t distribution with $n_1 + n_2 - 2$ degrees of freedom. Alternative analysis method: If the observed time measure Y has many outliers and the log transformation is not appropriate, the non-parametric Wilcoxon test will be used in place of the unpaired t-test. Given the pilot nature of this study, we make no power calculations; rather, effect size will be determined from analysis of these preliminary data.

Exempt and Expedited

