Scan condition: 20 RRMS patients will serve in the scan condition. All participants will be asked to refrain from eating 2 hours prior to their scheduled appointment. Participants will be scanned with MRS to derive brain temperature; fatigue will be measured with validated self-report fatigue questionnaires (FSS 46) and body temperature will be measured with an aural thermometer (Braun ThermoScan IRT 4520 Aural thermometer, consistent with our prior studies^{23,24}) immediately prior to scanning. We hypothesize that higher brain temperature in RRMS patients is correlated with worse fatigue. 10 patients will be randomized to aspirin group (standard dose, 650 mg in 1 pill), and 10 patients to placebo (placebo, 650 mg in 1 pill). After being administered aspirin/placebo, patients will have temperature measured aurally and then receive a scan. We hypothesize that brain temperature will decrease in the aspirin group compared to the placebo group. As a secondary outcome, we will examine change in fatigue after aspirin/placebo administration to see whether the aspirin group experienced a greater decrease in fatigue than placebo group. 12 healthy controls will be enrolled to obtain normative brain temperature. These subjects will fill out questionnaires, have temperature taken aurally, and receive a scan. After scanning, aural temperature will be measured and questionnaires filled out. All subjects will receive only 1 scan and only RRMS subjects will be randomized.

All MRIs will be read by study personnel for research purposes, and will also be read by a trained radiologist to screen for the presence of any IFs (incidental findings). If the radiologist sees an IF on a scan, the research team will contact the study subject immediately.

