Fatigue is among the most prevalent, debilitating, and refractory symptoms of multiple sclerosis (MS), a chronic autoimmune inflammatory disease affecting approximately 400,000 Americans that is typically diagnosed during young or middle adulthood. For persons with MS, fatigue limits functional independence and encumbers successful achievement of normative goals such as gainful employment and raising a family. Despite much empirical and clinical attention, the underlying mechanism(s) of fatigue are poorly understood. Investigations seeking a neuroanatomical basis for MS fatigue using MRI have produced equivocal results, with some studies finding no links, and others linking MS fatigue to such varied parameters as lesion load, corpus callosum atrophy,⁹ parietal atrophy, frontal atrophy, deep gray atrophy, and generalized cerebral atrophy. Inconsistent, non-specific findings perpetuate uncertainty about the etiology of MS fatigue as well as highlight the likelihood of multiple etiologies for MS fatigue. This notion is supported by the heterogeneity of patients' own descriptions of fatigue: some report stable fatigue, while others note day-to-day fluctuations. We currently lack effective treatments for fatigue. Although many patients are prescribed stimulant medication (e.g., modafinil) (likely based on the assumption that fatigue is linked to arousal dysfunction), several randomized clinical trials have failed to support their efficacy to reduce fatigue in MS. For this study, 20 relapsing-remitting multiple sclerosis patients and 12 healthy controls ages 18-65 will be recruited. They will undergo temperature readings, questionnaires, and an fMRI. This data will be used to establish the association of brain temperature and fatigue. We hypothesize higher brain temperature is correlated with worse fatigue.¹⁰ patients will be randomized to aspirin group (standard dose, 650 mg in 1 pill), and 10 patients to placebo (placebo, 650 mg in 1 pill). After being administered aspirin/placebo, patients will have temperature measured orally and then receive a scan. We hypothesize that brain temperature will decrease in the aspirin group compared to the placebo group. As a secondary outcome, we will examine change in fatigue after aspirin/placebo administration to see whether the aspirin group experienced a greater decrease in fatigue than

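### The documents conflict on whether a pre-dose scan exists; with the single post-dose scan in the procedures, the Aim 2 primary analysis and the Aim 3 change analyses cannot be run

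*Combined protocol and SAP*

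**What the plan says.** **Text that needs a pre-dose acquisition**
- Statistical Procedures, Aim 2. The primary analysis asks whether aspirin lowers brain temperature: "A 2x2 mixed ANOVA will be run with factors of group (placebo vs. aspirin) and time (Pre vs. Post".
- Statistical Procedures, Aim 3. The same ANOVA is applied to connectivity, with the prediction "We expect that aspirin (versus placebo) will increase network connectivity from pre- to post-scan". The plan then adds: "we will investigate whether the degree of change in network efficiency is correlated with degree of brain temperature change within the aspirin group".
- Research Questions, Aim 3, also describes resting-state connectivity as studied on both sides of dosing.

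**Text that provides one scan, after the pill**
- Procedures, Scan condition: "All subjects will receive only 1 scan and only RRMS subjects will be randomized". This is the only explicit count of scans.
- The same section: "After being administered aspirin/placebo, patients will have temperature measured aurally and then receive a scan".
- The Scientific Abstract repeats that order (with oral in place of aural temperature): "After being administered aspirin/placebo, patients will have temperature measured orally and then receive a scan".
- The methodology description in the Background section lists baseline measures, then the pill, then a one-hour scan. The step just before dosing is an ear temperature, not a scan: "Aural temperature will be recorded once again, just before the pill is administered (placebo or aspirin".

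**Text that works with one scan**
- Statistical Procedures, Aim 3: "For the full sample (N=20), regressions will be conducted to examine the association of brain temperature and FC within each network".
- The Aim 1 partial correlation of brain temperature with fatigue, controlling for sex, age and depression.

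**The concern.** Brain temperature and functional connectivity come only from the scanner, so a Pre value for either requires an acquisition before the pill. If the procedures are followed as one post-dose scan, the analysis named as primary for Aim 2 has no Pre data, and the plan does not say what replaces it. The substitute would then be chosen with data in hand, and a decrease or a change could be reported although no within-patient change was measured. If a pre-dose acquisition is intended, the procedures do not instruct staff to make it, and a missed one cannot be recovered once the pill is taken. The Subjects section lists the aspirin experiment as open with 10 of 60 patients enrolled (condition not given), so the question bears on patients still to be scanned.

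**Working it through.** The plan gives no sample-size or power figure for the scan condition, so there is no figure of its own to reproduce. The check is whether the planned effects can be estimated from the scheduled data.

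**Inputs.** 20 scanned patients, randomised 10 to aspirin and 10 to placebo (Procedures, Scan condition). Seven networks for connectivity (Statistical Procedures, Aim 3). Assumed, because not stated for this condition: a 95% confidence level and no dropout. The SD of brain temperature is not given, so results are in SD units.

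**1. Measures scheduled on both sides of the pill.** In the methodology description these are ear temperature, the hand dynamometer, and the questionnaires, including the fatigue VAS. Scanner measures are listed only after the pill.

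**2. Estimability of the ANOVA.** Code arm 0/1 (placebo/aspirin) and time 0/1 (Pre/Post). The cell mean is b0 + b1·arm + b2·time + b3·arm·time.
- With Pre and Post: 20 × 2 = 40 values per brain site, all four cells filled, rank 4 of 4. The interaction b3 is estimable.
- With Post only: 20 values per site. Time equals 1 in every row, so the time column repeats the intercept and the arm·time column repeats arm. The rank is 2 of 4. Only b0 + b2 and b1 + b3 can be estimated; the time effect and the interaction cannot be separated out.

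The same holds for connectivity in each of the seven networks.

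**3. Change correlation, aspirin group.** Each pair needs a connectivity change and a temperature change. With one scan per patient, neither exists: 0 of 10 pairs.

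**4. What remains.** Randomisation makes the expected pre-dose difference b1 zero, so the post-dose difference between arms is a valid estimate of the treatment effect. It is not a within-patient decrease. Its precision:
- Standard error = SD × √(1/10 + 1/10) = 0.447 SD
- t(0.975, 18 df) = 2.101
- 95% half-width = 2.101 × 0.447 SD = 0.94 SD

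This applies per brain site. Aim 1 names three sites; Aim 2 names none.

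**5. Other analyses.** The VAS fatigue ANOVA keeps both time points for all 20 patients. The Aim 1 partial correlation and the N=20 connectivity regression can be run, but on post-dose scans with half the patients on aspirin and no arm term in either.

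**The case against.** The strongest reply is that a pre-dose acquisition is implied. Procedures, Scan condition, runs in two steps: it first describes MRS with ear temperature taken right before scanning, and later describes a scan following the pill. The Research Questions section does much the same, and under Aim 2 has body temperature taken a further time before dosing. The Lay Abstract puts the MRI first and the aspirin second. This could describe a pre-dose run, or one session with the pill part-way through, which might still count as one scan.

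That stands as a possible intention, and it rules out the stronger inference that a pre-dose scan definitely does not exist. It does not remove the conflict. The two steps can equally be two aims describing the same scan, and the step-by-step order in the methodology description (pill, then scan) favours that reading. No text explicitly schedules a pre-pill acquisition.

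A reader might also infer from timing that only one scan is possible. A one-hour scan in a visit of under two hours leaves no room for a second full scan, but it does not exclude a short extra run, so timing does not settle the matter.

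Nor can Pre and Post simply be taken as early and late runs within the scan hour. No text says so, both would follow the pill, and the Research Questions section speaks of connectivity before dosing.

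Finally, this is a pilot without power calculations. That excuses low precision; it does not supply the missing cells.

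**Conclusion.** The contradiction is in the text and must be resolved before further patients are scanned. The claim that the analyses cannot be run is conditional: it holds if the procedures are carried out as one post-dose scan. In that case the time effect, the group-by-time interaction and the change correlation cannot be estimated (rank 2 of 4; 0 of 10 pairs), and a 10 versus 10 post-dose comparison remains, with a half-width of about 0.94 SD per site at the assumed 95% level and without dropout.

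A reader might infer that the study can then say nothing about aspirin, or that the whole study fails. The documents do not support that. The randomised post-dose comparison is valid, and the VAS fatigue ANOVA and the exercise analysis are unaffected. Aim 1 can still be run, though it would need to account for treatment arm. The problem concerns the 20 patients in the scan condition, out of 60 planned patients.

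**What to change.** State, consistently in the methodology description, Statistical Procedures, Procedures, Research Questions, Scientific Abstract and Lay Abstract, how many MRS and resting-state acquisitions each patient has and when each occurs relative to the pill. Then match the analysis.

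**If a pre-dose acquisition is intended** (including a pre-dose run, pill and post-dose run within one session): schedule it in the procedures, and clarify the one-scan statement and the visit length. The planned ANOVAs and change correlation then stand. Cost: an extra acquisition per patient and possibly a longer visit. Any patient already scanned only once lacks the pre-dose value.

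**If one post-dose scan stands:**
- Replace the Aim 2 and Aim 3 ANOVAs on scanner data with between-arm comparisons of post-dose brain temperature and connectivity. Covariate adjustment is optional. If used, name the covariate in advance; the last ear temperature before the pill is one candidate, but the documents give no correlation between ear and brain temperature from which to judge its value.
- Drop the change correlation.
- Add treatment arm to the Aim 1 partial correlation and to the N=20 connectivity regression.
- Reword hypotheses about decrease or change as post-dose differences from placebo.

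Cost: a text change only, but within-patient change, and whether connectivity change follows temperature change, are no longer tested.
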